2 OBJECTIVES

The primary objective of the study is as follows:

- To determine if TD-9855 has an acute (Parts A and B) and sustained (Part C) pressor response and improves symptoms of orthostatic intolerance in subjects with nOH due to MSA, PAF, or Parkinson's disease.

The secondary objective(s) of the study is as follows:

- To evaluate the safety and tolerability of TD-9855 in subjects with nOH.
- To evaluate the PK and PD (NE and DHPG) of TD-9855 after single and multiple doses in subjects with nOH.

3 STUDY DESIGN

[figure not shown]
3.1 Overview

This is a multicenter, randomized, 3 part, single-blind (Part A), double-blind (Part B), and open-label multiple dose extension (Part C) study of TD 9855 versus placebo in subjects with nOH. However, beginning with Amendment 2 of this protocol, Part B of the study has been discontinued. Therefore, any new subjects enrolled after Amendment 2 will not be enrolled in Part B. Details regarding Part B are still included in this document but where appropriate the reader is referred to the prior version of this protocol for more specific information related to Part B.

This study now consists of 2 Parts, A and C. Part A follows a daily, single, escalating dose design starting with placebo on Day 1, followed by a dose of [REDACTED] TD-9855 on Day 2, and proceeding to escalating higher doses of TD-9855 on a daily basis up to a maximum dose of [REDACTED] based on safety, tolerability, and determination of a pressor effect. In Part C, subjects who demonstrate a pressor effect in Part A, who complete Part A, and remain otherwise eligible will have the option to receive open-label TD-9855 by tablet daily for up to [REDACTED]

Study Schematics

[figure not shown]
Part A – Single Blind, Dose-Escalation

Part B

Beginning with Amendment 2, Part B has been discontinued. Refer to prior versions of this protocol regarding more specific information pertaining to Part B.

Part C

3.2 Rationale for Study Design

This study is designed to evaluate the acute (Part A and B) and sustained (Part C) efficacy and safety of TD-9855 in improving BP and reducing orthostatic symptoms in subjects with nOH. The study should provide important information between BP, orthostatic symptom relief and the potential correlation with changes in NE and dihydroxyphenylglycol (DHPG) release. The information to be learned could be useful in optimizing diagnosis and clinical management. Safety and tolerability will be assessed throughout the study treatment period via laboratory measurements (eg, hematology, chemistry, and urinalysis) and monitoring of AEs.

3.3 Selection of Doses and Regimen

This study aims to evaluate the effects of single and multiple doses of TD-9855 on systolic blood pressure, symptoms associated with nOH, safety, and tolerability. The current doses of TD 9855 for this trial were chosen using pharmacokinetic (PK) and pharmacodynamic (PD) modeling to achieve a range of NET inhibition and to determine a minimum dose required to yield an increase in sitting systolic blood pressure. An ascending dose design was chosen in Part A to allow the subjects to start at a low dose because of the intrinsic hyper adrenergic responsiveness in these patients. The maximum dose levels ([REDACTED] single dose or [REDACTED] multiple doses QD) were selected to provide maximal steady state NET inhibition in all subjects despite inter-individual PK variability. A single dose of [REDACTED] and multiple doses QD of [REDACTED] are below or equal to doses examined and tolerated in single and multiple dose studies in healthy volunteers respectively. The maximum dose in Part C [REDACTED] QD) is equal to the well-tolerated [REDACTED] dose that was studied in two Phase 2 trials in patients with ADHD and FM where [REDACTED] was administered over 6 to 8 weeks.

3.4 Study Endpoints

3.4.1 Primary and Secondary Endpoints

For Part A, the primary study endpoint is the change from time-matched placebo in seated systolic blood pressure at 6 to 8 hours after drug administration. For Part C, the primary endpoint is the improvement from baseline in the Likert scale “dizziness, lightheadedness, feeling faint, or feeling like you might black out” (OHSA, question 1) at week 4.

The secondary endpoints for Part A include:

- Improvement in the Likert scale for “dizziness, lightheadedness, feeling faint, or feeling like you might black out” (OHSA, question 1).
- The composite OHSA score.
- Change from time-matched placebo in standing SBP
- Change from time-matched placebo in seated SBP (area under the curve for 0-12 hours following drug administration).
- Duration of standing during the orthostatic standing test

The secondary endpoints for Part C include:

- The composite OHSA and OHDAS score.
- Change from time-matched placebo in standing SBP
- Change from time-matched placebo in seated SBP (area under the curve for 0-12 hours following drug administration).
- Duration of standing during the orthostatic standing test

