This is a multicenter, randomized, 3 part, single-blind (Part A), double-blind (Part B), and open-label multiple dose extension (Part C) study of TD-9855 versus placebo in subjects with nOH. However, beginning with Amendment 2 of this protocol, Part B of the study has been discontinued. Therefore, any new subjects enrolled after Amendment 2 will not be enrolled in Part B. Details regarding Part B are still included in this document but where appropriate the reader is referred to prior version of this protocol for more specific information related to Part B.

This study now consists of 2 Parts, A and C. Part A follows a daily, single, escalating dose design starting with placebo on Day 1, followed by a dose of [REDACTED] TD-9855 on Day 2, and proceeding to escalating higher doses of TD-9855 on a daily basis up to a maximum dose of [REDACTED] based on safety, tolerability, and determination of a pressor effect. In Part C, subjects who demonstrate a pressor effect in Part A, who complete Part A, and remain otherwise eligible will have the option to receive open-label TD-9855 by tablet daily for up to [REDACTED]

Study Procedures:

Part A – Dose Escalation

On Day -2 of Part A, eligible subjects will be admitted to the clinical research center (CRC), where they will remain during the entire dose escalation period. On Day 1, subjects will receive a single dose of placebo in a single-blind manner (ie, subject remains blinded). This will be followed by daily single-blind dose escalations, beginning with [REDACTED] of TD-9855 on Day 2. On each subsequent day, subjects will receive a single escalating dose of TD-9855

PROTOCOL SYNOPSIS (CONTINUED)

[REDACTED] [Day 3], [REDACTED] [Day 4], [REDACTED] [Day 5]) until Day 5 or until reaching the preset stopping criteria described below, whichever occurs first. The stopping criteria are:

- A determination from the Investigator (in collaboration with the Sponsor) that administration of the subsequent dose may pose a safety concern
- SBP \geq 180 mm or DBP \geq 110 mm in the sitting position replicated 2 more times over an hour
- Intolerable side effects as determined by the Investigator
- Received maximum dose of study medication specified by the protocol

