15. History of cancer within the past 2 years other than a successfully treated, non-metastatic cutaneous squamous cell or basal cell carcinoma or cervical cancer in situ.
16. Gastrointestinal condition, which in the Investigator's judgment, may affect the absorption of study drug (eg, ulcerative colitis, gastric bypass).
17. Any major surgical procedure within 30 days of dosing on Day 1.
18. Any other significant cardiovascular, pulmonary, renal, endocrine, hepatic, neurologic, psychiatric, immunologic, hematologic, gastrointestinal, or metabolic disease not currently controlled with medical treatment (eg, a stable medication dosing regimen).
19. Currently receiving any investigational drug or have received an investigational drug within 30 days of dosing on Day 1. An investigational drug is defined as non-FDA approved drug.
20. Allergic to or unable to drink apple juice (Part A only).
21. Any condition or laboratory test result which, in the Investigator's judgment, might result in an increased risk to the subject, or would affect their participation in the study.
22. Additionally, the Investigator has the ability to exclude a subject if for any reason they feel the subject is not a good candidate for the study or will not be able to follow study procedures.

Test Product, Dose, and Route of Administration; Regimen; Duration of Treatment:

Detailed storage and preparation instructions for test product will be provided in a separate pharmacy manual.

Reference Therapy, Dose, and Route of Administration; Regimen; Duration of Treatment:

In Parts A (and previously in Part B which was discontinued), placebo solution for individual subject administration will be prepared to match TD-9855 doses but will not contain TD-9855. Details regarding placebo preparation will be provided in a separate pharmacy

PROTOCOL SYNOPSIS (CONTINUED)

manual. Part C is open-label and all eligible subjects will receive active TD-9855.

Study Evaluations

Safety Assessments:

- Adverse events (AE) [including serious adverse events (SAE)], clinical laboratory tests (including hematology, serum chemistry, and urinalysis), vital signs (including supine blood pressure), 12-lead ECGs, use of concomitant medications, and physical examination will be used to assess safety.

Efficacy Assessments:

- Efficacy assessments include measurement of seated and standing systolic blood pressure and completion of Orthostatic Hypotension Symptom Assessment (OHSA) questionnaire.

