Visit number	Admit		Treatment period									Follow-up		
	1		2	3	4	5	6	7	8	9	10	11 EOS		
Study week (beginning of week except Day 140)				1	2	3	4	5	9	13	17	20	23	25
Procedure (Study Day)	Admit Day -2	Day -1 ^b	Day 1 ^b	Day 2 ^b	Day 8	Day 15	Day 22	Day 29	Day 57	Day 85	Day 113	Day 140 ^m	Day 155	Day 169
Overnight Residency	X ^a	X ^a	X ^a											
Informed Consent	X													
Review Inclusion/Exclusion Criteria	X	X												
Medication and Medical History	X ^c													
Weight/BMI & Temperature	X	X	X	X		X		X		X		X	X	X
Orthostatic Standing Test including supine blood pressure ^d		X ^d	X ^d	X ^d		X ^d		X ^d		X ^d		X ^d	X ^d	X ^d
Supine blood pressure ^e	X ^e				X ^e		X ^e		X ^e		X ^e			
24 hour blood pressure monitoring ^f		X ^f				X ^f		X ^f		X ^f				X ^f
ECG (12-lead)		X												X
Physical Examination ^g		X ^g	X ^g	X ^g		X ^g		X ^g		X ^g		X ^g	X ^g	X ^g
Urine Pregnancy Test ^h	X ^h													
Safety labs: Hematology, Chemistry, and UA	X ^o													X
PK Sampling ⁱ			X ⁱ	X ⁱ		X ⁱ		X ⁱ		X ⁱ		X ⁱ		X ⁱ
DHPG Sampling ^j			X ^j	X ^j				X ^j						
NE Sampling ^k			X ^k					X ^k						
OHQ (OHSA and OHDAS) ^l		X ^l	X ^l	X ^l	X ^l	X ^l	X ^l	X ^l	X ^l	X ^l	X ^l	X ^l	X ^l	
Clinician's/Subject's Global Impression ^l		X ^l	X ^l	X ^l	X ^l	X ^l	X ^l	X ^l	X ^l	X ^l	X ^l	X ^l	X ^l	
Concomitant Medications	X	X	X	X	X	X	X	X	X	X	X	X	X	X
Adverse Events	X	X	X	X	X	X	X	X	X	X	X	X	X	X
Study Drug Administration ^m			X ^m	X ^m	X ^m	X ^m	X ^m	X ^m	X ^m	X ^m	X ^m	X ^m	X ^m	
Subject Satisfaction Survey ⁿ			X ⁿ			X ⁿ		X ⁿ				X ⁿ		
Telephone Assessments (highlighted in gray)					X		X		X		X			

SCHEDULE OF STUDY ASSESSMENTS (CONTINUED)

- a. Subjects will admit to the research unit on Day -2 and remain resident through the completion of study procedures on the morning of Day 2.
- b. The timing of Day -1 "postdose" assessments should be prospectively calculated, based on the target Day 1 dosing time (eg, orthostatic standing test and Clinical Impression and OHQ assessments). Study Day 1 is defined as the day of first study dosing with TD-9855 in Part C. On Day 2 subjects are discharged from the research facility after all study procedures are completed the morning of Day 2.
- c. History update, if any changes since participation in Part A (and B if appropriate) of the study.

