- d. The orthostatic standing test will be performed in the morning before eating breakfast at approximately the same time of day each visit under fasting conditions after midnight to avoid the confounding effect of post-prandial hypotension. In addition, at least 4 hours after dosing (but no more than 7 hours) and before lunch, the standing test will be repeated. At each time point, BP and HR measurements will be recorded with automated (or manual) sphygmomanometer while supine at 5 and 10 min (with the torso and head elevated 30 degrees from horizontal), after seated at 5 and 10 min and after 1, 3, 5, and 10 min while standing. The standing time will be measured with a chronometer and the duration of standing will be recorded. More details related to the sequence of dosing and orthostatic assessments are described below. For the Day 155 and 169 assessments, the timing of the "postdose" orthostatic test should be calculated based on the Day 1 dosing time.
- e. On Days 8, 22, 57 and 113, supine blood pressures will be collected twice in the morning before eating (after 5 and 10 minutes resting at 30° elevation), and twice again at least 4 hours after dosing (but no more than 7 hours and before lunch) after 5 and 10 minutes resting at 30° elevation. On Day -2, supine blood pressures should be measured (after 5 and 10 minutes resting at 30° elevation).

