3.5 Minimization of Bias

Bias will be minimized through the use of randomization and blinding.

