8.2 Efficacy Variables

Primary Efficacy Endpoint

For Part C, the primary endpoint is the improvement from baseline in the Likert scale "dizziness, lightheadedness, feeling faint, or feeling like you might black out" (OHSA, question 1) at week 4. A responder in Part C is defined as a subject who demonstrates at least a 2 unit decrease (improvement) from baseline in the OHSA question 1 at week 4. The raw data is in ordinal scale and will be treated as continuous variable to get the descriptive statistics.

Secondary Efficacy Endpoint

The secondary endpoints for Part C include:

- Change from baseline in the composite OHSA, OHDAS, and OHQ score
- Change from baseline in standing SBP
- Change from baseline in seated SBP
- Duration of standing during the orthostatic standing test
- Change from Supine SBP to Seated SBP

For the Supine and Seated blood pressure, the summary table will be based on the average value of the 5 minutes and 10 minutes measurements. The composite OHSA score is calculated by the non-missing average score of the 6 OHSA items. Similarly for the composite OHDAS score is the non-missing average of the 4 items. The composite OHQ score is the average of the OHSA and OHDAS composite scores.

For Change from time-matched placebo in seated SBP, calculate the area under the effect curve from 0 to 12 hours (AUC0_12) using the following trapezoidal rule. Calculation of AUC0_12 will use observed data points (actual time). If there is missing data for seated SBP, AUC will not be calculated. Here is the formula for AUC:

$$AUC_{0-t} = \frac{\sum_{i=1}^{I-1} (y_i + y_{i+1})(t_{i+1} - t_i)}{2}.$$

where

 y_i = the value of the parameter at the i-th time point,

 t_i = the i-th time point, and

I = the number of time points used in the AUC calculation.

A hypothetical example is given below to illustrate the calculation.

			Al	UC Calcula	tion	
Nominal Time Point (H)	Actual Time Point (H)	Parameter Value (Y_i)	T_diff= T_(i+1) - T_i	Y_sum= Y_(i+1) + Y_i	T_diff x Y_sum	AUC _{0_12}
0	0	1.5				
4	2.01	2.2	2.01	3.7	7.437	
7	3.91	3.4	1.9	5.6	10.64	
9	8.05	2.8	4.14	6.2	25.668	
12	23.95	2.1	11.87	4.8	56.976	50.361

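### Part C is given placebo-referenced and 0–12 h AUC blood pressure endpoints that its design does not supply; the Part C SAP keeps the AUC rule with a miscalculated example and uses a baseline that is not clock-matched for pre-lunch readings

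*Protocol*

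**What the plan says.** **Protocol, Part C endpoints.** Section 3.4.1, repeated in the synopsis, lists four Part C secondary items. Two refer to placebo: "Change from time-matched placebo in standing SBP", and "Change from time-matched placebo in seated SBP (area under the curve for 0-12 hours following drug administration"). Both repeat the Part A items.

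**Protocol, placebo.** The synopsis text on reference therapy states: "Part C is open-label and all eligible subjects will receive active TD-9855". The only placebo day in the current design is in Part A: "On Day 1, subjects will receive a single dose of placebo in a single-blind manner".

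**Protocol, measurement times.** In Part A (Table 1, footnote f) the orthostatic test is done in the morning and again 4, 7, 9 and 12 h after each dose. In Part C (Table 2, footnote d) it is done fasting before breakfast, and then "at least 4 hours after dosing (but no more than 7 hours) and before lunch, the standing test will be repeated". Footnote b adds that on Day -1 the timing of the assessments that correspond to post-dose ones, the orthostatic test among them, is fixed in advance: the "assessments should be prospectively calculated, based on the target Day 1 dosing time".

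**SAP (Part C only, section 1).** Sections 5.1 and 8.2 list change from baseline in standing and in seated SBP, with no AUC. Section 9.2.2 summarises them at pre-breakfast and pre-lunch. Section 6.2 sets the baseline for blood pressure, heart rate and standing duration at pre-breakfast on Day 1. For the OHQ and global impression scores it uses pre-lunch on Day -1. Section 8.2 then adds: "For Change from time-matched placebo in seated SBP, calculate the area under the effect curve from 0 to 12 hours". It specifies the trapezoidal rule on actual times, no AUC when a seated SBP is missing, and a worked example.

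**The concern.** An endpoint should be obtainable from the design and schedule that are meant to produce it. Here the protocol names a comparator that Part C does not contain and a 12-hour curve that its schedule does not sample. The SAP has moved to change from baseline but still carries the AUC instruction, so protocol and SAP disagree, and the SAP disagrees with itself. Anyone who reused the AUC text, for Part A for example, and checked code against the example would be checking against a wrong number.

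The change-from-baseline endpoint has a weakness of its own. Pre-lunch is the only post-dose test of each visit, so it is where an effect of that day's dose would show. Under SAP 6.2 it is compared with a fasting reading taken at another time of day.

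**Working it through.** **1. Can Part C give a 0–12 h seated AUC?**

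| | Part A, each dosing day | Part C, each visit with an orthostatic test |
|---|---|---|
| Placebo day | Day 1 | none |
| Test times | predose, 4, 7, 9, 12 h | predose, and once between 4 and 7 h |
| Share of 0–12 h spanned | 12/12 = 100% | 4/12 = 33% to 7/12 = 58% |

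Part C has no 9 h or 12 h reading. Under the SAP's own rule that a missing seated SBP means no AUC, the number of Part C subjects evaluable for AUC0_12 is 0.

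The 24-hour monitoring in Part C (Protocol 6.3.10) reads every 2 hours, but it does not fill the gap as planned. Posture is logged rather than fixed as seated, the equipment depends on the site, and SAP 9.2.3 plans only outlier counts, a listing and individual plots from it.

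**2. Standing SBP against placebo.** Part C subjects have completed Part A dosing (inclusion criterion 11), so each should have Part A Day 1 standing readings on placebo in the morning and at 4, 7, 9 and 12 h. A within-subject reference near the Part C 4–7 h test could in theory be taken from there. Neither document says that it will be. The reference is unspecified, not unobtainable.

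**3. The SAP 8.2 example.** The formula is AUC = Σ (y_i + y_(i+1)) × (t_(i+1) − t_i) / 2. The inputs are actual times 0, 2.01, 3.91, 8.05 and 23.95 h, with values 1.5, 2.2, 3.4, 2.8 and 2.1.

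The printed figure first: (7.437 + 10.64 + 25.668 + 56.976)/2 = 100.721/2 = 50.3605. The stated 50.361 therefore follows from the printed product column. The fault is in the last row.

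| Last row | Printed | From the example's inputs |
|---|---|---|
| Interval | 11.87 | 23.95 − 8.05 = 15.90 |
| Sum of values | 4.8 | 2.8 + 2.1 = 4.9 |
| Product | 56.976 | 15.90 × 4.9 = 77.91 |

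Corrected: (7.437 + 10.64 + 25.668 + 77.91)/2 = 121.655/2 = 60.83. The printed value is 1 − 50.361/60.8275 = 17% too low.

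The corrected total runs to 23.95 h, so it is still not a 0–12 h area, and the SAP gives no rule for stopping at 12 h. With linear interpolation:
- value at 12 h: 2.8 − 0.7 × 3.95/15.90 = 2.626
- last product: 3.95 × (2.8 + 2.626) = 21.433
- AUC: (7.437 + 10.64 + 25.668 + 21.433)/2 = 32.59

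Nominal times (0, 4, 7, 9, 12 h) give (14.8 + 16.8 + 12.4 + 14.7)/2 = 29.35. None of these readings gives 50.361.

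**4. The pre-lunch comparison.** Let B be pre-breakfast and L pre-lunch. Under SAP 6.2 the pre-lunch change at visit v is

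BP(v, L) − BP(Day 1, B) = [BP(v, L) − BP(Day -1, L)] + [BP(Day -1, L) − BP(Day 1, B)].

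The first bracket is the clock-matched change. The second is a difference between two pre-dose readings at different times of day, one fasting and one after breakfast. It contains no Part C treatment. The documents give no figure for its size or direction, so none is assumed. It can be avoided because Table 2 schedules the orthostatic test on Day -1 and footnotes b and d time its second session to match the post-dose one. The pre-breakfast change uses a pre-breakfast baseline and is already matched.

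**The case against.** The strongest reply is that the SAP has already dealt with this. Sections 5.1, 8.2 and 9.2.2 use change from baseline, and the list of tables and figures in SAP Appendix 2 contains no AUC and no placebo-change output. The example is labelled hypothetical, the analyses are descriptive (9.2.4), and the primary endpoint, OHSA question 1 at week 4, is not touched. All of that stands. It limits the harm to the specification. It does not remove the contradiction between protocol and SAP, or the one within SAP 8.2.

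A reader might infer four stronger things that the documents do not support:

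- **That neither placebo-referenced endpoint can be computed.** This is true of the AUC only, because Part A Day 1 could serve for standing SBP.
- **That planned Part C tables would be empty.** No planned output depends on either placebo comparison.
- **That the SAP changed the endpoints without explanation.** Part of the SAP was not available for this review, and the protocol's text on analysing the secondary endpoints is redacted. An explanation may exist.
- **That time-matching is lost altogether.** Only the pre-lunch comparison loses it.

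**Conclusion.** The point holds with limited reach. Two of the four protocol secondary endpoints for Part C are defined against a comparator that Part C lacks. For the seated AUC the number of evaluable subjects is 0. For standing SBP the reference is undefined. SAP 8.2 contradicts the SAP's own endpoint list, and its example is 17% low against its own inputs (50.361 against 60.83), with an integration range about twice the 12 h in its label. The SAP baseline leaves every pre-lunch change in blood pressure and standing duration open to a time-of-day and meal difference whose size the documents do not give.

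These conclusions rest on the Part C schedule in Table 2 as printed and on the 24-hour monitoring not being used as a seated series, which matches SAP 9.2.3. No trial result is shown to be wrong.

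A minor related point concerns Protocol 3.5, which states: "Bias will be minimized through the use of randomization and blinding". Part B, the randomized part, is discontinued. Part A gives placebo and then ascending doses in a fixed order, and Part C is open-label, so neither remaining part is randomized.

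**What to change.** 1. **Protocol 3.4.1 and synopsis.** Replace the two placebo-referenced Part C items with change from baseline in standing SBP and change from baseline in seated SBP, without AUC.
2. **SAP 6.2.** For pre-lunch blood pressure and standing duration, use the Day -1 test at the matched clock time as baseline. Keep pre-breakfast Day 1 as baseline for pre-breakfast readings. This must be made together with item 1, so that protocol and SAP mean the same thing by baseline. The subgroups in SAP 7.3 and the baseline summaries in 9.1.2 should then state that they use pre-breakfast Day 1, and the increase-from-baseline categories in 9.3.4 should say which baseline applies at each time point.
3. **SAP 8.2.** Delete the AUC paragraph and example. If the text is reused for Part A, correct the last row (15.90, 4.9, 77.91, total 60.83) and add a rule that ends the integration at 12 h, which gives 32.59 for the same inputs with linear interpolation.
4. **Protocol 3.5.** Say that the remaining Parts A and C are not randomized.

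The cost is wording and one additional derived baseline. No new data are needed. A subject without the second Day -1 test would have no pre-lunch change, since SAP 6.4 does not impute. The 0–12 h AUC is given up for Part C, where it could not be obtained.
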